9 ADVERSE EVENTS AND DEVICE DEFICIENCIES

9.1 Definitions of Events

9.1.1 Adverse Events (AEs)

An AE is defined as any untoward medical occurrence, unintended disease or injury, or untoward clinical signs (including abnormal laboratory findings) in participants, users or other persons, whether or not related to study device [ISO14155:2011(E)].

Pre-existing conditions should be considered as part of the participant's medical history and should not be reported as an AE unless there is a substantial increase in severity or frequency of the condition, which has not been attributed to natural history. Exacerbation of an existing condition should be reported as an AE if the event meets the protocol definition of an AE.

9.1.2 Serious Adverse Events (SAEs)

A serious adverse event is defined by ISO 14155 and/or 21 CFR 803.3 as an adverse event that:

- a. led to death;
- b. led to serious deterioration in health that resulted in life-threatening illness or injury, resulted in permanent impairment;
- c. required inpatient hospitalization/prolonged hospitalization, or resulted in medical/surgical intervention to prevent life-threatening illness/injury or permanent impairment; or
- d. led to fetal distress, fetal death, or a congenital abnormality or birth defect.

9.1.3 Adverse Device Effect (ADE) / Serious Adverse Device Effect (SADE)

An adverse device effect is defined as any adverse event that is considered to be related to the use of an investigational medical device. This definition includes any event resulting from insufficiencies or inadequacies in the instructions for use, deployment, implantation, or operation or any malfunction of the investigational device (study device) and includes any event that is a result of a user error.

A serious adverse device effect (SADE) is defined as an ADE that has resulted in any of the consequences characteristic of an SAE.

9.1.4 Unanticipated (Serious) Adverse Device Effect (UADE/USADE)

An unanticipated (serious) adverse device effect (UADE/USADE) is any (serious) adverse device effect on health or safety or any life-threatening problem or death caused by, or associated with, a study device, which by its nature, incidence, severity, or outcome has not been identified in the current instructions for use and/or current version of the risk analysis report, or any other unanticipated serious problem associated with a device that relates to the rights, safety or welfare of participants.

UADEs/USADEs will be reported to all applicable regulatory authorities as per the respective regulatory authority guidelines.

9.2 Severity of Adverse Events

Each AE shall be assessed for its severity, or the intensity of an event, experienced by the participant according to the criteria below.

Severity Rating	Description
Mild	Event, signs, or symptoms that do not interfere with the participant's daily activity, are usually considered self-limiting, can be treated with non-prescription type medications, and do not require medical intervention
Moderate	Event may interfere or cause low level inconvenience with the participant's daily activity. Requires medical intervention and/or treatment; however, unlikely to require hospitalization or be considered potentially life-threatening in nature
Severe	Event may cause significant discomfort to the participant and/or interferes with the participant's daily activity. Requires medical intervention and/or treatment to preclude a permanent impairment; may be life threatening and/or require hospitalization

9.3 Relationship of Adverse Event to Device(s)/Procedure

Each AE will be assessed for its relationship to the study device or procedure according to the following guidelines.

A. Assess each AE for its relationship to the device or procedure.

- Device Related: This category should be restricted to AEs directly attributable to the study device used.
- Procedure: A procedure includes any study-related activity performed.

B. The following categories shall be used for assigning the certainty of the relatedness.

Relatedness	Description
Not Related	Event is independent of study intervention and/or evidence exists that the event is related to another etiology. There must be an alternative etiology documented by the clinician.
Unlikely Related	Event in which the temporal relationship to study intervention makes a causal relationship improbable (e.g., the event did not occur within a reasonable time of the study device use) and in which underlying disease provides plausible explanations (e.g., the participant's clinical condition other concomitant treatments).
Likely Related	Event in which there is evidence to suggest a causal relationship and the influence of other factors is less likely. The event occurs within a reasonable time after use of the study device and is less likely to be attributed to concurrent disease.
Related	Event in which there is clear evidence to suggest a causal relationship and other possible contributing factors can be ruled out. The event occurs in a plausible time relationship to use of the study device and cannot be explained by concurrent disease.

9.4 Reporting of Events

In this study, AE collection will be limited to those occurring in the arm in which the study device is inserted, as well as any other undesirable clinical event judged to be related or possibly related to the study device, or

a study procedure regardless of anatomical region an event that, in the opinion of the investigator warrants reporting.

The Investigator must report any AEs which are serious, unanticipated/unexpected and probably or possibly related to the study product or procedures to the reviewing HREC in accordance with the relevant HREC reporting requirements.

The Investigator may also have additional responsibilities for AE reporting to their governing Health Authority which they are responsible for identifying and fulfilling.

For all adverse events collected, all sections of the appropriate Case Report Form (CRF) must be completed.

All SAEs, SADEs, and/or UADEs/USADEs must be reported to the Sponsor within one (1) working day of the site/investigator becoming aware of the event.

De-identified copies of all requested relevant documentation should be submitted to the Sponsor within 72 hours of knowledge, as appropriate.

The Sponsor will provide results of any evaluation of an unanticipated/unexpected adverse product effect to appropriate Regulatory/Health Authorities and to all Investigators within the respective reporting timelines, after the Sponsor is notified of the event. The PI will assume responsibility for submitting reports of evaluation results to their relevant HREC. The PI must notify the Sponsor in writing the report has been submitted to HREC and must retain evidence of their compliance with this requirement.

BD will comply with all other Sponsor safety reporting requirements and timelines for other entities and local health authorities in other countries where this study or other studies with the same product are being conducted, in compliance with study procedures and applicable local regulatory requirements and BD Standard Operating Procedures.

9.4.1 Pregnancies

Investigators must instruct participants to inform them immediately if they become pregnant during the trial.

In case of a pregnancy during the participation in the trial, the participant will be immediately considered for premature discontinuation.

The pregnancy will be registered on the CRF protocol deviation form. In addition, the Pregnancy Form (which is independent of the CRF) will be completed with all the available information within the same time frame and following the same routing as for a SAE, described previously.

All pregnancies discovered by the Investigator after the termination of the trial but which were initiated during the participation in the trial will be reported to BD as occurring during the trial.

9.5 Adverse Event (AE) Management

Collection of adverse events will begin after the participant has signed the Consent Form through the end of the participants participation in the study.

The participant will be questioned in an open-ended manner regarding any new or worsening undesirable signs or symptoms they may have experienced since starting the study. Signs and symptoms must be

comprehensively documented on the appropriate source documentation. All related signs and symptoms should be grouped under one diagnosis if possible.

Each sign, symptom, disease or illness reported must be evaluated by the Investigator or designee to determine if it meets the definition of an AE.

Any worsening or undesirable signs or symptoms of the PIVC insertion sites that results in the withdrawal of the participants from the study or, in the opinion of the Investigator or designate, warrants medical attention or medication will be considered AEs that will be subjected to the same criteria as all other AEs. Overall medical coverage for study participants will be provided by Griffith University affiliated general practitioners (GP), e.g. GPs at Griffith University Health Clinic and emergency physicians at the Gold Coast University Hospital.

If an AE or SAE occurs around the PIVC insertion site, it may be needed to take photographs of the site only. Only the Principal Investigator, Sub-investigator, study staff and Sponsor will have access to the de-identified photographs for review and assessment.

9.5.1 Follow-up of Adverse Events (AE)

Adverse events that are ongoing at the time of the participant's scheduled completion visit will be followed until resolution of the event means of the investigational site contacting the participant via telephone or by any other means considered appropriate. The Investigator will communicate with the sponsor Medical Monitor (via telephone and/or email) as to the need for further follow-up. In the case of discrepancies, the Investigator's judgement will prevail. All communications with the participant and medical monitor will be documented appropriately.

The clinical course of any serious adverse event will be followed according to accepted standards of medical practice until the event resolves, stabilizes, or in the opinion of the Investigator, is no longer considered clinically significant as it relates to the study product and/or study procedures.

9.5.2 Additional procedures for Assessing & Reporting Serious Adverse Events (SAE)

SAE criteria are specified in Section 9.1. All SAEs must also be assessed by the Investigator and Sponsor Medical Monitor to determine whether an SAE is expected or unexpected. An adverse event will be considered unexpected or unanticipated if the nature, severity or frequency of the event is not consistent with the risk information previously described in the protocol, Informed Consent, Information for Use (IFU) or Investigator's Brochure.

All adverse events, regardless of the Investigator's opinion of expectedness or relationship to the study product, must be reported to the Sponsor and Safety vendor, in case sponsor should consider outsourcing any safety management or reporting tasks, within 24 hours. The Investigator or designee must report the event by telephone or email to the Study Monitor. In addition, the Investigator must notify the local Field Assurance team within 24 hours of the receipt of the information about any device-related (unlikely related, likely related, related) AEs and SAEs by sending the completed AE/SAE form to the following email address: [contact]

Medical questions about study safety issues and serious adverse events can be directed to the Sponsor Medical Monitor.

[name]
VP, Medical Affairs, BDTI, Medical
Affairs
Office: +1- [contact]
[contact]
e-mail: [contact]

9.6 Device Deficiencies

The Investigator will record a device deficiency if a device used in the study procedure failed to meet its performance specifications whether due to mechanical failure, malfunction, or defect. Device deficiencies also include use errors and inadequate labeling. This applies to: devices used to treat the participant, or devices in which the package was opened, but the device was not used for treatment, or devices with which treatment was attempted, but the device did not remain through the entire study procedure/period.

All mechanical failures, malfunctions, missing components, and defects of the study devices must be promptly reported to the Sponsor within 24 hours; **notification by email** ([contact]) with copy to Sponsor Study Monitor and Sponsor local representative. Information required: Product Code; Batch/Lot; Date of event; Did the event occur before, during or after use; Description of the event; Did an adverse event occur. In all events, the device(s) in question should be returned to the Sponsor as instructed by the Sponsor monitor or sponsor appointed local representative, for analysis. If it is not possible to return the device(s), the reason it could not be returned as well as its final disposition should be documented.

If the device deficiency was associated with an AE, the reporting provisions for AEs, ADEs, SAEs, SADEs and UADEs/USADEs apply.

Reported deficiencies will be investigated and reported under 21 CFR part 803 Medical Device Reporting by the Sponsor if necessary. The site may be contacted to provide additional information to allow the Sponsor to conduct a thorough investigation.

It is the responsibility of the Investigator to notify the responsible HREC of such device deficiencies in accordance with the HREC reporting requirements.

10 STATISTICAL METHODS

10.1 Overview of Study Design

This is a single-centre, open-label, multi-visit, self-controlled study design, in ~40 healthy participants, randomized by cannula gauge of peripheral intravenous catheter (PIVC) device into the lower arm cephalic vein of both arms.

More details about the statistical methods used for primary, secondary and exploratory objectives will be provided in a separate Statistical Analysis Plan (SAP). This SAP will include mock tables and figures whenever possible.

10.2 Sample Size Considerations

There is limited published data investigating the impact of PIVC catheter length on indwell time; a single article was found in the literature comparing catheter survival between a BD PIVC catheter (20 gauge; 4.78 cm/1.88 inch length) and midline catheter (POWERWAND™, 19.5 gauge; 6 cm/2.3 inch length)⁹. The indwell time results for this research were utilized to calculate a sample size estimate. As this an exploratory study no statistical justification for sample size is required; however, an estimate was compiled to provide an initial assessment of potential sample requirements. Based on the available dataset, a sample size of ~20 participants per PIVC gauge would be required given median failure times of catheter lengths at 1 and 3 days (Figure 2)

[figure not shown]

Figure 2. Details of estimation of sample size calculation.

10.3 Analysis Population

The following populations are defined as:

Population	Description
Enrolled	All participants who sign the ICF
Evaluable	All participants who complete the study until either the catheter fails or the protocol is completed (i.e., 72 hours)

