8 PARTICIPANT DISCONTINUATION/WITHDRAWAL

8.1 Discontinuation/Withdrawal

- A participant may withdraw from the study at any time at his/her own request or may be withdrawn at any time at the discretion of the investigator or sponsor for safety, behavioral, compliance, or administrative reasons. This is expected to be uncommon.
- At the time of discontinuing from the study, any indwelling catheters will be safely removed and disposed of in accordance with the Instructions For Use as per standard protocol without any data collected. Additionally, the sites of insertion will be assessed for signs of infection and extravasation. The participant will be followed-up within 96 hours for participant safety and to ensure no adverse events have occurred following removal of indwelling catheters.
- If the participant withdraws consent for disclosure of future information, the sponsor may retain and continue to use any data collected before such a withdrawal of consent.
- If a participant withdraws from the study, he/she may request destruction of any samples taken and not tested, and the investigator must document this in the site study records.

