8.3 Patient replacement

Any participants lost to the current study (withdrawn or lost to follow-up) will be replaced through normal screening processes and allocated to the incomplete experimental group to ensure at least 20 participant completers for each catheter gauge. Replacement participants will be started in the same order as drop-out/withdrawal; drop-outs will not be considered eligible for readmission due to potential effects of prior catheter placement on subsequent study outcomes.

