10.4 General Considerations

Participants who have withdrawn consent for continuation of the study (i.e., dropouts or non-compliant) will be included in the analysis by modern imputation methods for missing data. In the unforeseen circumstance of a protocol violation (e.g., 20G PIVC instead of 22G PIVC; blood was collected into 6mL vacutainer before 2mL for a specific participant), the data will be analyzed ‘as treated’ – that is, data will be analyzed as the participant’s actual received intervention. However, in the unforeseen circumstance of a protocol violation whereby a participant receives the wrong intervention (e.g., two different gauge catheters; two 20G catheters of the same length), they will be treated as per protocol and thus their data will be excluded from the study.

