2.4 Sample Size

There is limited published data investigating the impact of PIVC catheter length on indwell time; a single article was found in the literature comparing catheter survival between a BD PIVC catheter (20 gauge; 4.78 cm/1.88-inch length) and midline catheter (POWERWAND™, 19.5 gauge; 6 cm/2.3-inch length). The indwell time results for this research were utilized to calculate a sample size estimate using the routine “Survival - Two Survival Curves - Logrank Tests” available in the software PASS 2019. Based on the available dataset, a sample size of ~20 participants per PIVC length would be required, considering median failure times of catheter of different lengths of 1 and 3 days, as can be seen in Figure 2.4.1. The same calculation will be applied to investigating the impact of increased gauge, because the increased volume of catheters is similar in both condition (i.e., 1 versus 1.75 inch = 75% increased volume; 20 versus 22 gauge = 51% increased volume).

Figure 2.4.1: Details of sample size calculation

Logrank Tests

Numeric Results for the Logrank Test in Terms of Sample Size

Alternative Hypothesis: Two-Sided

Power	N1	N2	N	Haz Ratio (HR)	Ctrl	Trt	Acc-rual Pat'n	Acc-rual Time/Total Time	Ctrl Loss	Trt Loss	Ctrl to Trt		Alpha	Beta
					Med Surv Time (M1)	Med Surv Time (M2)					to Trt	to Ctrl		
0.8054	19	20	39	0.3333	1.00	3.00	Equal	0 / 3	0.0000	0.0000	0.0000	0.0000	0.0500	0.1946

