5.2.5 Approaches and Analyses for Missing Data and Other Data Issues

[figure not shown]
Missing data will not be imputed and will be considered missing for data analysis, resulting in a possible reduced sample size.

6 Summary of General Study Data

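### Protocol 10.4 imputes withdrawn participants, SAP 5.2.5 forbids imputation, and neither document names the primary analysis set or says how a catheter removed at withdrawal enters the survival analysis.

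*Protocol*

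**What the plan says.** - **Analysis set.** Protocol 10.3 defines Enrolled and Evaluable, the latter as "All participants who complete the study until either the catheter fails or the protocol is completed (i.e., 72 hours". Neither Protocol 10.5 nor SAP 5.2.1.1 says which one the primary analysis uses. SAP 6.1 refers to SAP 4.1 for population membership, but 4.1 covers only deviations in device or tube order.
- **Withdrawn participants.** Under Protocol 10.4 those who withdraw consent "will be included in the analysis by modern imputation methods for missing data". SAP 5.2.5 states: "Missing data will not be imputed and will be considered missing for data analysis". SAP 6.2.1 adds that a participant who misses two subsequent visits has all data excluded.
- **Replacement.** Under Protocol 8.3 a new participant is "allocated to the incomplete experimental group to ensure at least 20 participant completers for each catheter gauge".
- **Discontinuation.** Protocol 8.1 has the catheters removed "in accordance with the Instructions For Use as per standard protocol without any data collected", with a site check and follow-up within 96 hours.
- **Site symptoms.** Protocol 9.5 foresees and classes as an AE "Any worsening or undesirable signs or symptoms of the PIVC insertion sites that results in the withdrawal of the participants from the study".
- **Failure.** Protocol 7.6 and SAP 6.6 count two things as failure: loss of flush or draw, and removal on a doctor's assessment of an AE. SAP 5.2.1.1 identifies the event from the blood-draw and flush variables only.

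**The concern.** Whether a participant completes is known only after insertion and can depend on how the catheter performs. An analysis set defined by completion, and topped up with people who did complete, would lose some catheters that did badly and make indwell time look longer than it was. With about 20 participants per gauge, a few such losses are visible. Leaving the choice open until data are in hand also means that the primary set could be chosen with the results known. Imputing failure times is no better: a survival analysis can use the time observed up to withdrawal, and the protocol names no method.

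**Working it through.** **1. The plan's own figure.** SAP 2.4 uses the PASS routine "Survival - Two Survival Curves - Logrank Tests" with "Alternative Hypothesis: Two-Sided", alpha 0.05, 19 and 20 catheters, medians of 1 and 3 days (hazard ratio 1/3), 3 days of follow-up and zero loss in both groups.
- Failure by 72 hours under exponential survival is 1 − exp(−3 ln 2 / median): 0.875 (short) and 0.500 (long).
- Expected events: 19 × 0.875 + 20 × 0.500 = 26.625.
- Schoenfeld power: Φ(√(26.625 × 19/39 × 20/39) × ln 3 − 1.96) = Φ(2.833 − 1.960) = 0.809. The Lakatos method gives 0.8058.
- The stated value is 0.8054, so it reproduces. It is not in dispute, but it allows for no withdrawals.

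**2. The rules side by side.** Take a participant who asks to leave on Day 2 because one site hurts, with both catheters still patent.

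| Rule | What happens to this participant |
|---|---|
| Protocol 7.6 | Failure only if a doctor's AE assessment leads to removal |
| SAP 5.2.1.1 | No event in either case: no AE-removal variable is listed |
| Protocol 10.3 | Without a failure, not Evaluable |
| Protocol 10.4 | Included, by imputation |
| SAP 5.2.5 | Not imputed |
| Protocol 8.3 | Replaced; does not say whether the data are kept |

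The direct contradiction is Protocol 10.4 against SAP 5.2.5. Protocol 10.4 would also conflict with an Evaluable-only analysis, if one were intended. Protocol 10.1 says only that the SAP gives more detail, which does not settle precedence. Protocol 10.3 also speaks of one catheter although each participant has two, so a participant with one failed catheter who then withdraws is unclassified.

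**3. Size if withdrawn participants are excluded and replaced.** The documents give no withdrawal rate. Assume the planning medians, independent failure times in the two arms, and a share s of failures that surfaces as a self-requested withdrawal. Among those retained, observed failure is F(1 − s)/(1 − sF). The chance that a participant withdraws is P = 1 − (1 − 0.875s)(1 − 0.5s), and about 20P/(1 − P) are replaced per gauge.

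| s | Short (true 87.5%) | Long (true 50.0%) | Difference (true 37.5 points) | Replaced per gauge |
|---|---|---|---|---|
| 5% | 86.9% | 48.7% | 38.2 | 1.5 |
| 10% | 86.3% | 47.4% | 38.9 | 3 |
| 20% | 84.8% | 44.4% | 40.4 | 7 |
| 30% | 83.1% | 41.2% | 41.9 | 12 |

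Simulation (1,500 runs per setting, 20 pairs) gives median hazard ratios of 0.318, 0.308 and 0.287 for s = 10%, 20% and 30%, against about 0.32 to 0.33 when the withdrawals count as failures. Here the length effect is enlarged.

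**4. A scenario that goes the other way.** Suppose 22 start in one gauge, 2 withdraw for symptoms at the 1-inch site, and the 20 completers have 10 short and 6 long failures. Completers only: 10/20 − 6/20 = 20 points. Counting the 2 as short failures: 12/22 = 54.5% against 6/22 = 27.3% to 6/20 = 30%, a difference of 24.5 to 27.3 points. Here exclusion shrinks the length effect.

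**5. Other treatments, same assumptions as step 3.**
- Censoring at withdrawal keeps the hazard ratio at about 0.32 to 0.34. Simulated power is 0.73, 0.70 and 0.61 for s = 10%, 20% and 30%, against 0.83, 0.80 and 0.77 when counted as failures (Monte Carlo standard error about 1 point).
- Leaving participants out without replacement gives Lakatos power of 0.813 with 20 per length, 0.793 with 19, 0.771 with 18, 0.748 with 17 and 0.722 with 16.

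**The case against.** Several stronger readings are tempting, and the documents do not support them.

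- **That all the rules exclude one another.** Protocol 8.3 sets a recruitment floor and does not say that replaced participants' data are dropped. Replacement and imputation could both be done.
- **That site-symptom withdrawals will vanish.** Neither document ties Evaluable to the primary analysis. Mock listing C.0.5 keeps catheters ending before 72 hours with status 0 (28.76 and 37.93 hours, for example), and mock Table A.4.1 counts 20 per configuration. That points to censoring. It is dummy data and not a rule, but it is fair evidence of intent.
- **That doctor-directed removals are lost by definition.** They are failures under Protocol 7.6, and Protocol 7.10.1 refers a suspected AE to a clinician. By definition only a withdrawal without that decision escapes. The remaining gap is the SAP 5.2.1.1 coding.
- **That nothing is known about a withdrawal.** AE forms must be completed (Protocol 9.4), SAP 6.1 records the stage reached, SAP 5.2.3.1 tabulates removal reasons, and flush and draw records are dated. A last patent time should exist. What is not secured is the removal time and the reason by arm.
- **That the bias favours a particular length.** Steps 3 and 4 of the check go in opposite directions.
- **That concealment is lost for the gauge comparison.** Refilling by gauge affects only the replacements. Changing it would trade against balanced groups, and it is a separate matter.

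It also stands that Protocol 8.1 expects withdrawal to be uncommon, and that this is a feasibility study without acceptance criteria.

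**Conclusion.** The concern holds as a conflict and a gap. Protocol 10.4 and SAP 5.2.5 cannot both be followed, and no text names the primary analysis set or the treatment of a catheter removed at withdrawal. Overstated indwell time is conditional: it needs the Evaluable set to be the one analysed, and withdrawals for site symptoms without a doctor's removal decision. Under the assumptions of step 3 the understatement of 72-hour failure is about 1 point or less for each catheter at s = 5%, rising to about 4 points (short) and 9 points (long) at s = 30%. It is nil with no withdrawals. The direction for the length contrast cannot be stated in advance. Separately, AE removals that Protocol 7.6 and SAP 6.6 call failures may be missed, because SAP 5.2.1.1 does not code them. This should be corrected before database lock; it does not undermine the design.

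**What to change.** 1. **Primary set.** State in Protocol 10.3 and SAP 4.1 that the log-rank and Cox analyses use all randomised participants with catheters inserted, whether or not they complete, apart from the wrong-device exclusions already stated. Replacements add to this set and substitute for nobody. In SAP 6.2.1, let missed visits lead to censoring at last patent access for the primary endpoint instead of exclusion, and say how the tampering and respiratory-infection exclusions there apply to this set.
2. **Missing data.** Delete the imputation sentence in Protocol 10.4. A catheter removed at withdrawal that does not meet Protocol 7.6 is right-censored at its last successful flush or draw.
3. **Events.** Add the AE-removal event to SAP 5.2.1.1 so that it agrees with Protocol 7.6 and SAP 6.6. Because censoring for site symptoms may be informative, add a sensitivity analysis that counts such a withdrawal as failure of that arm's catheter. Keep this out of the primary analysis: counting a patent catheter as failed would change the endpoint.
4. **Data at removal.** In Protocol 8.1, replace the no-data wording with recording of removal date and time, reason by arm and status at last access, unless the participant refuses.

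The cost is wording in both documents and a few CRF fields at a removal that takes place anyway. Gauge groups may end slightly unequal, and indwell times may look slightly shorter.
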